Official Title: Glyburide vs Glucovance in the Treatment of GDM

NCT Number: NCT02726490

Document Date: 06/05/2018

Title: Glyburide vs Glucovance in the treatment of gestational diabetes

PI: [name]

**Abstract:** This study will be a randomized open label trial of glyburide compared to glucovance in the management of gestational diabetes. We hypothesize that glucovance will provide improved glycemic control and a lower failure rate with no increase in neonatal adverse outcomes. Sixty-seven patients will be randomized by computer to each arm of the study. Outcomes will be glycemic control, failure rate of the drug to achieve glycemic goals, and neonatal outcomes.

**Lay abstract:** Two medications which can be taken by mouth are usually used to treat patient with gestational diabetes. The names of those medications are glyburide and metformin. Both of these medications have been shown to be safe for use in pregnancy. This study would like to compare the drug glyburide, to a drug that is a combination of glyburide and metformin to see which one is better at helping patients to keep their blood sugar at normal levels. Patients who participate in the study will be assigned to take one of the drugs being studied. As part of the study, the levels of blood sugar that is measured in the morning and after meals will be stored in a computer program as well as information about the babies weight at birth, amount of sugar in the babies blood at birth, and if there are any complications during the delivery .

**OBJECTIVE:** To compare glyburide to glucovance for treatment of gestational diabetes

**SPECIFIC AIM #1:** To compare glycemic control in patients treated with glucovance to glycemic control in patients treated with glyburide.

We hypothesize that glucovance will be superior to glyburide in achieving euglycemia.

**SPECIFIC AIM #2:** To compare the maternal outcomes of hypoglycemia and drug failure rate in patients treated with Glyburide to glycemic control in patients treated with glucovance.

We hypothesize that glucovance will have a similar rate of hypoglycemia and a lower rate of drug failure requiring initiation of insulin therapy.

**SPECIFIC AIM #3:** To compare the neonatal outcomes of gestational age at delivery, birthweight, fetal anomalies, neonatal hypoglycemia, APGAR scores and admission to the NICU in patients treated with glyburide to patients treated with glucovance.

We hypothesize that neonatal outcomes will be similar between the two groups

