### *Data analysis*

Patient outcomes will be compared between groups. The initial analysis of the dichotomous outcome (oral medication failure) will involve the creation of a 2 x2 contingency table and the use of a chi-square or Fisher's exact test as appropriate. A risk ratio (RR) for the outcome of drug failure comparing the two medications will be calculated from a log-binomial regression models using the GENMOD Procedure. The RR will be reported along with a 95% confidence interval and P value. If confounding is detected then an adjusted RR will be calculated. Additionally, glucose and dietary diaries will be analyzed.

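### The hypotheses of similar hypoglycemia, similar neonatal outcomes and no increase in neonatal harm have no margin, interval estimate or analysis that could support them

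*Combined protocol and SAP*

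**What the plan says.** All references are to the combined protocol and SAP.

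- **Abstract.** The trial hypothesis joins better glycemic control with "a lower failure rate with no increase in neonatal adverse outcomes".
- **Specific Aim #2.** "We hypothesize that glucovance will have a similar rate of hypoglycemia", alongside a lower rate of drug failure.
- **Specific Aim #3.** The outcomes are "gestational age at delivery, birthweight, fetal anomalies, neonatal hypoglycemia, APGAR scores and admission to the NICU". The hypothesis is "We hypothesize that neonatal outcomes will be similar between the two groups".
- **Sample size calculations.** Sixty-seven women per arm, from drug failure rates of 31% and 10% with 80% power. No other outcome is sized.
- **Data analysis.** The general statement is "Patient outcomes will be compared between groups". The specific one is "The initial analysis of the dichotomous outcome (oral medication failure) will involve the creation of a 2 x2 contingency table", followed by a chi-square or Fisher's exact test and a log-binomial risk ratio with 95% confidence interval and P value, all for drug failure.

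For hypoglycemia and the neonatal outcomes, the text available for review contains no margin, definition of similar, named test, interval estimate or power statement. It also gives no rule for reading a non-significant result.

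**The concern.** A prediction of similarity needs either a margin to test against or an interval that shows how large a difference remains possible. The plan provides neither for the outcomes where it predicts similarity. All that is left is an unspecified comparison between groups, and failing to find a difference in 134 women is weak evidence that none exists.

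What is at stake is the safety conclusion. The Background says that the combined product has not been studied in pregnancy, that glyburide has been associated with higher birth weight, macrosomia and neonatal hypoglycemia, and that hypoglycemia is glyburide's major side effect. Several of these are the outcomes predicted to be similar. A statement of no increase that the data cannot bear could be taken as reassurance about fetal safety.

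**Working it through.** **Inputs from the documents.** 67 per arm; failure rates of 31% and 10%; 80% power; Fleiss method with continuity correction (all from Sample size calculations).

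**Assumptions.** Two-sided 5% level, which the plan does not state but which matches its 95% interval. Baseline harm rates of 2%, 5%, 10%, 20% and 30%, because the documents give none. All 134 women contribute data.

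**1. The plan's own figure.** With mean rate 0.205 and difference 0.21:

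n = [1.96·√(2·0.205·0.795) + 0.842·√(0.31·0.69 + 0.10·0.90)]² / 0.21² = (1.119 + 0.464)² / 0.0441 ≈ 56.8.

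Continuity correction: (n/4)·[1 + √(1 + 4/(n·0.21))]² ≈ 66.0. If 56.8 is first rounded up to 57, the result is 66.2, which rounds up to 67. The stated size reproduces, but for drug failure only.

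**2. Power to detect a doubling.** This is the sum of the two binomial probabilities (67 per arm, rates p and 2p) over all pairs of counts where the uncorrected chi-square test rejects at 5%.

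**3. Interval width.** With equal rates, the half-width of the 95% interval on the risk difference is 1.96·√(2p(1−p)/67). At 10% this is 1.96·√(0.18/67) = 0.102.

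| Assumed baseline | Expected events per arm at baseline | Power for a doubling | Doubling missed | 95% interval, equal rates |
|---|---|---|---|---|
| 2% | 1.3 | about 8% | about 92% | ±5 points |
| 5% | 3.4 | about 20% | about 80% | ±7 points |
| 10% | 6.7 | about 36% | about 64% | ±10 points |
| 20% | 13.4 | about 72% | about 28% | ±14 points |
| 30% | 20.1 | about 94% | about 6% | ±16 points |

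If Fisher's exact test were used instead, power at 2%, 5% and 10% would be about 1.5%, 11% and 29%. The normal-theory interval is rough at 2%, where only one or two events per arm are expected.

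The last column also shows what equal observed rates would leave open. At 2%, 5% and 10% the upper limit reaches or passes a doubling (+5 against 2, +7 against 5, +10 against 10). At 20% and 30% it does not (+14 against 20, +16 against 30), although the interval is wider in absolute terms.

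**4. Risk-ratio scale at 10% in both arms.** SE(log RR) = √(2·0.9/(67·0.1)) = 0.518, so the 95% interval is exp(±1.96·0.518) = 0.36 to 2.76.

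**5. Continuous outcomes (birthweight, gestational age).** Half-width = 1.96·√(2/67) = 0.34 SD. Detectable difference at 80% power = (1.96 + 0.842)·√(2/67) = 0.48 SD.

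**6. What a margin would require, as illustration only.** For an assumed 10-point non-inferiority margin, 10% in both arms, one-sided 0.025 and 80% power: n = (1.96 + 0.842)²·2·0.1·0.9/0.1² ≈ 142 per arm. At 67 per arm the power for that margin is about 49%.

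**The case against.** The strongest reply is that the plan contains no such error. Each aim is to compare, the similarity statements are expectations, and comparing the groups meets the aims. It is tempting to infer that the investigators will read p > 0.05 as proof of similarity, but the documents nowhere say so. What stands is narrower: the plan states the hypotheses and specifies no valid way of supporting them.

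Four other strong readings also go too far.

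- *That difference tests have been assigned to the harm outcomes.* Chi-square and Fisher's tests are named for drug failure only. For hypoglycemia and the neonatal outcomes no test is named at all.
- *That real harm would almost certainly be missed.* That is fair only near the 2% baseline. At 10% a doubling is missed about 64% of the time, and at 30% about 6%. Maternal hypoglycemia may be fairly common, given fasting and post-meal testing each day over an estimated 6 to 26 weeks, so the missed-doubling argument may have little force there.
- *That two of the three aims are similarity claims.* Aim 2 also predicts a lower failure rate, the one outcome for which the trial is sized.
- *That the two drugs together are untried in pregnancy.* The Background says they are often used together as separate doses; the combined product is what it calls unstudied.

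It is also fair to say that secondary outcomes need not be powered. This point asks for no extra power. The no-increase claim, however, sits beside efficacy in the abstract's hypothesis, and Aim 3 has a hypothesis of its own. Since the plan already promises an interval for drug failure, extending that practice is a small step.

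**Conclusion.** The point holds for Aim 3, the hypoglycemia half of Aim 2 and the abstract's no-increase clause. The trial is sized for drug failure, and without a margin or interval estimates the plan gives these predictions no valid support. A non-significant comparison would not provide it.

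The size depends on event rates that the documents do not give. For outcomes at 10% or below, a doubling would be missed more often than found, and equal observed rates would still leave one possible. For outcomes at 20% to 30% the problem is smaller. For birthweight and gestational age the data would fix the difference to within about a third of an SD either way.

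The figures assume complete data. The Method section limits infant data to what is in the mother's chart, so the neonatal intervals may be wider. This is a gap that should be closed; it does not invalidate the drug-failure comparison.

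**What to change.** - In the aims, restate the Aim 2 hypoglycemia hypothesis and the Aim 3 hypothesis as estimation of the difference between arms.
- In the abstract, remove the no-increase clause from the hypothesis.
- In Data analysis, commit to reporting, for each of these outcomes, the risk difference (mean difference for birthweight and gestational age) with its 95% confidence interval and the largest increase that the interval does not exclude. State in advance how Apgar scores will be summarised.
- In the same section, state that a non-significant P value will not be reported as similarity or as no increase.

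The cost is wording and a few more intervals, with no extra patients or data. The downside is a weaker permitted safety claim.

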## **BACKGROUND**

Gestational diabetes (GDM) is defined as carbohydrate intolerance with onset or first recognition during pregnancy. It is estimated that gestational diabetes affects 2-10% of all pregnancies. The national and state

prevalence rates are estimated to be 9.2% and 3-10%, respectively. It is estimated that border regions such as El Paso, Texas have a 10-15% prevalence rate. A study performed by the Department of OB/GYN at Texas Tech University Health Sciences Center El Paso found that the prevalence of GDM in El Paso was 8.7%.

Gestational diabetes is a problem worldwide and in El Paso, and is increasing. It is estimated that the prevalence of GDM is 1:50 to 1:20 pregnancies. It is more common Native Americans, Hispanics and Blacks. There has also been an increase in the incidence of GDM in the last decades. This increase has been attributed to the increased obesity and type 2 diabetes rates. Women who are diagnosed with GDM are at higher risk for complications during pregnancy and delivery, and also have an increased risk of developing type 2 diabetes after delivery. Additionally, the fetus is at risk for macrosomia and neonatal hypoglycemia. The rates of GDM vary depending on race. Pregnant Hispanic (5.4%) and African American (5.4%) females are at higher risk of developing GDM compared to non-Hispanic white. Furthermore, Hispanic women who were born in Mexico and live in a border region have a prevalence rate of 10-15%.

GDM is diagnosed by a two-step testing process. In step one the patient receives a 50g glucose load with determination of blood glucose levels one hour later. If the one hour value is  $\geq 130\text{mg/dl}$ , patient receives a second glucose challenge of 100g. Blood glucose is checked prior to the 100g load, and at one hour, two hours and three hours. Expected values are 95mg/dl, 180mg/dl, 160mg/dl and 145mg/dl. Two values that meet or exceed these expected values are considered diagnostic of gestational diabetes.

The typical approach to the management of GDM is by proper diet and exercise. When blood sugar levels are not maintained within normal levels with diet and exercise, then a medication regimen is necessary. The American College of Obstetrics and Gynecology (ACOG) guidelines suggest that oral medications as well as insulin are suitable for the treatment of GDM. Literature also, suggests that it is not necessary for patients to use insulin for the treatment of GDM prior to the use of oral medications.

Pregnant women are no more or less compliant than other diabetics. It is well documented that the use of oral agents improves compliance and is easier to dose. The failure rate of both glyburide and metformin during pregnancy has been studied. The failure rate of glyburide in pregnancy is 16-20%. The failure rate of metformin in pregnancy is 34-40%. The failure rates of glyburide and metformin have not been studied locally.

Glyburide is an antihyperglycemic agent in the sulfonylurea class. It has been used in pregnancy since 2000 when a landmark paper was published demonstrating the efficacy and safety of its use in pregnancy. Glyburide is FDA pregnancy category B indicating that it may safely be used in pregnancy. Glyburide works by activating the ATP-sensitive potassium channels in pancreatic beta cells which stimulates insulin release. The major side effect associated with glyburide is hypoglycemia. This problem is common to all antihyperglycemic agents and is not unique to glyburide. This effect can be ameliorated with close attention to correct caloric intake. Glyburide should not be used in patients with sulfa allergies.

Metformin is FDA pregnancy category B indicating it is considered safe for use in pregnancy. Metformin is a biguanide antihyperglycemic agent which works by increasing sensitivity to the action of insulin. Metformin

has minimal risk of hypoglycemia. The most common side effect is gastrointestinal upset which usually resolves within one week of medication initiation.

Glucovance is a drug combination of glyburide and metformin (aka glucophage). Both glyburide and metformin have been studied individually in pregnancy and are often used together in pregnancy as separate doses of each drug. The combined drug, glucovance, has not been studied in pregnancy. Glyburide and metformin have complementing mechanisms of action, so patients who take glucovance may have better glycemic control.

Oral antidiabetic drugs have been found suitable for the management of gestational diabetes because of their ability to provide good glycemic control when used properly. It is known that glyburide and metformin do cross the placenta, but there are no recorded long-term studies that have shown the implications of in utero exposure to these drugs.

[figure not shown]
Current literature notes that glyburide has been associated with higher neonatal birth weight, neonatal hypoglycemia, increased macrosomia (Jiang et al., 2015). No studies indicated increased fetal death associated to the use of oral blood sugar medications. Glyburide and Metformin have been studied extensively for use in pregnancy; however there are no published studies on the use of the combination drug glucovance during pregnancy. The failure rate for metformin and glyburide used as single agents is relatively high. The purpose of this study is to see if the combination drug has a lower failure rate. The proposed study will compare glyburide and glucovance in the treatment of gestational diabetes.

**STUDY DESIGN:** A randomized open label study of patients with GDM not controlled with diet.

Patients will be randomized to either glucovance or glyburide. Sixty-Seven patients are required in each arm.

**METHOD:**

All patients presenting to the Diabetes in pregnancy clinic at Texas Tech HSC with a diagnosis of gestational diabetes who fail dietary management will be invited to participate in the study. Failure of dietary management is defined as 20% of values which exceed the expected goals of fasting  $\leq 95$ mg/dl and 1hour postprandials  $\leq 140$ mg/dl over a 2 week period. All patients of the OB/Gyn Diabetes clinic who fail dietary management are given the standard treatment for gestational diabetes, which consists of a regimen of oral antidiabetics (glyburide or metformin), unless contraindicated by patients' medical history or physicians assessment. If diabetes is not controlled with oral medication, defined as 20% of values which exceed the expected goals of fasting  $\leq 95$ mg/dl and 1hour postprandials  $\leq 140$ mg/dl over a 2 week period, then the patient is offered insulin as part of the treatment. See Figure 1 below for an outline of possible options for patients.

**Figure 1.** Possible options for treatment of GDM of patients in the OB/Gyn Diabetes clinic.

In this study patients will be invited to participate in a randomized open label trial of Glucovance and glyburide. Participants have to be above the age of 18, and be between 12-32 weeks pregnant. Participants will be asked to sign an informed consent and a HIPPA authorization for release of medical record information for the purpose of monitoring patient safety and medication effectiveness. The forms will be explained to the subject in their preferred language, and will be asked if they have any questions and if they understand the study. After informed consent is obtained, patients will be randomized to either a glyburide or glucovance group.

All patients will receive counseling on diet and exercise by a registered nurse (RN) in the clinic, as well as information on daily self-monitoring of blood glucose. The Department of OB/GYN does not employ a registered dietician (RD), but the RN in the GDM clinic has received education on nutrition and diet in diabetes and will work closely with the perinatologist. Any informational sheets that are provided to the patient will be given in their preferred language and will be thoroughly explained by the RN and physician, and will be given the opportunity to ask any questions that they may have.

Each patient will purchase their own blood monitoring devices, but will be shown how to perform proper self-monitoring of blood sugar at home. Patients are instructed to check their blood sugars following the steps below: (See patient information sheet)

1. Wash your hands with soap and warm water
2. Insert a test strip into your meter.
3. Use your lancing device on the side of your fingertip to get a drop of blood. (Gently squeezing and

- massaging your finger before pricking can increase blood flow)
4. Touch and hold the edge of the test strip to the drop of blood, and wait for the result. (Do not remove the test strip until results appear on display screen).
  5. Your blood glucose level will appear on the meter's display.
  6. Compare your results to the glucose range.
    - a. Fasting= 60-95 mg/dL
    - b. 1 hour AFTER meals= 60-140 mg/dL
  7. Any out of range blood sugar levels (high or low) should be reported to your MFM by calling the OB/Gyn clinic at [contact], or notifying the MFM at the next medical visit.

Subjects will be instructed to take medication as prescribed, and informed on the signs and symptoms of hypoglycemia (see sample GDM information guide). Furthermore, the subjects will be instructed to take a fast acting carbohydrate food (see list of foods) for blood sugars 60 mg/dL or below, and will be encouraged to seek emergency care for persistent blood sugars below 60 mg/dL after treatment with food. If hypoglycemia does occur, the participants will be instructed to call the OB/Gyn clinic and notify MFM at the time of their next appointment. Patient's blood sugar and meal journal/record will be reviewed to identify any persistent high or low blood sugars.

Prenatal care will be performed in the diabetes in pregnancy clinic staffed by a maternal-fetal medicine specialist and by residents in obstetrics and gynecology. Decisions regarding medication changes will be made by the attending maternal-fetal medicine specialist.

Participants will be in the study until they deliver. The estimated length of time in the study is between 6 and 26 weeks depending on gestational age at the time of enrollment. Study participants will be followed up during their normal clinic visits. The frequency of clinic visits will vary depending on the need of every subject, but there will be about 7-12 visits and each will be approximately 1 hour long.

The medications, glyburide or glucovance, will be provided to the participants at no cost during the time they are in the study or until they deliver. Medications will be dispensed by any of the UMC Outpatient Pharmacies. Participants will be given information about the pharmacies available and their hours of operations (see patient pharmacy information handout).

The funds to purchase these medications come from the department of OB/GYN, and no funding will be provided by any pharmaceutical company. The Prescriptions will be identified on the prescription with a unique study identifier. During the study duration, monthly reports will be generated to identify those prescriptions pertaining to the study and monthly bills will be generated, for those identified prescriptions. (For details on pricing and dosage please refer to attached email)

Participants who withdrawal from the study or who are no longer taking the study medication (such as other oral medications or insulin), will be responsible for the cost of their medications.

Subjects may have potential side effects or allergy to medication. Each patient will be given a generic information sheet from the pharmacy that indicates the side effects and signs and symptoms of an allergic

reaction to the medication. Also, the potential side effects will be discussed with the patient by the MFM at the time the medications are being prescribed. (See attached information sheet for glucovance and glyburide) Patients will be encouraged to notify PI of any side effects noted while taking the medication. Any side effects reported by the patient or noted through medical records will be documented and reviewed promptly and reported as required to IRB and/or FDA.

Participant medical charts (Texas Tech and UMC) will be reviewed to obtain information on fetal and maternal complications, outcomes, drug dosages, side effects, and gravida and para will be collected for analysis. (See data collection sheets for detailed variable list) Only infant information available in the mother's chart will be abstracted.

Medication Side Effects (per pharmacy patient information sheet, the information sheet may be revised by the pharmacy at any time)

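### The self-monitoring steps let a woman hold a low glucose value until her next visit; limiting that option to high values is a cheap safety edit

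*Combined protocol and SAP*

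**What the plan says.** All the text at issue is in METHOD, in the numbered self-monitoring steps and the paragraph after them.

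- **Step 6** gives the target ranges: "Fasting= 60-95 mg/dL" and "1 hour AFTER meals= 60-140 mg/dL". A low value is therefore one below 60 mg/dL.
- **Step 7** sets the reporting rule: "Any out of range blood sugar levels (high or low) should be reported to your MFM". This is done by telephoning the clinic, "or notifying the MFM at the next medical visit".
- **The next paragraph** opens with "Subjects will be instructed to take medication as prescribed" and says that women are "informed on the signs and symptoms of hypoglycemia". It then tells them to "take a fast acting carbohydrate food (see list of foods) for blood sugars 60 mg/dL or below", and encourages emergency care if values stay below 60 mg/dL after food. The reporting rule follows: "If hypoglycemia does occur, the participants will be instructed to call the OB/Gyn clinic", and the specialist is also to be told at the next appointment. The paragraph ends with a review of the glucose and meal record for persistent highs or lows.

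A later paragraph of METHOD leaves medication changes to the attending maternal-fetal medicine specialist and says that visit frequency depends on the patient's needs.

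**The concern.** Step 7 joins its two routes with an *or*; the hypoglycemia paragraph joins its two with an *and*. A woman working through the numbered steps finds low values named expressly in step 7, and finds that she may wait. If she reads on, she finds that hypoglycemia calls for a telephone call, but not whether a low reading without symptoms counts as hypoglycemia.

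What is at stake is how soon the clinic learns of a low value. BACKGROUND names hypoglycemia as the major side effect of glyburide, and both arms contain glyburide. The woman is told to keep taking the drug as prescribed and the specialist decides on changes, so a low value that nobody at the clinic has yet heard of or seen cannot prompt a look at the dose.

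**Working it through.** No arithmetic applies. The check sets the two instructions side by side and tests them under each meaning of hypoglycemia.

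| | Step 7 | Hypoglycemia paragraph |
|---|---|---|
| Trigger | Any value outside the step 6 range, so below 60 mg/dL on the low side | Hypoglycemia, with no number attached |
| Telephone the clinic | One of two options | Instructed |
| Tell the specialist at the next visit | The other option, sufficient alone | Instructed in addition to the call |

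**Meaning 1: hypoglycemia is a low reading.** Position supports this. The call sentence comes directly after the 60 mg/dL rules on carbohydrate and emergency care, and directly before the record review for high or low values. On this meaning one event, for example a fasting value of 55 mg/dL, has an optional call in step 7 and an instructed call a paragraph later. The two instructions differ.

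**Meaning 2: hypoglycemia is an episode with symptoms.** The opening of the paragraph supports this, since it speaks of signs and symptoms. The two rules then have different triggers and can both be followed. But a fasting value of 55 mg/dL without symptoms falls under step 7 alone, and its report may wait.

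**Common result.** On either meaning, a woman who follows step 7 as written may hold back a low value without symptoms. Only on meaning 1 do the two instructions differ.

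**What cannot be settled.** The material under the medication side-effects heading was not available to this review, nor were the patient information sheet and the GDM information guide that METHOD cites. Any of them may define hypoglycemia or state a call rule.

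**Effect on the trial's results.** Under *Sample size calculations*, drug failure rests on values that miss the goals of at most 95 mg/dL fasting and at most 140 mg/dL one hour after meals. Low values do not enter. The reporting instructions make no distinction between arms.

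**The case against.** The strongest reply is that a specific rule governs a general one. Step 7 is a catch-all, and much of its traffic will be routine highs such as a fasting 96 mg/dL. The hypoglycemia paragraph is the specific rule. A woman who follows it by calling has also used the first option of step 7, so nothing that one rule requires is forbidden by the other. This stands as an answer to a reader who infers that the protocol flatly contradicts itself: it does not, and the two differ at all only on the first meaning. It helps less with a patient who follows numbered steps that name low values in so many words.

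The second reply is that the clinical risk is already handled. Carbohydrate and emergency care are instructed whichever reporting route she takes. Both arm descriptions require daily recording of glucose with diary copies kept, and the specialist discusses side effects when prescribing. A report at the next visit is still a report. All of this stands, and it keeps the point minor. It does not replace a timely call: the food treats the episode, the record review has no stated timing and looks for persistent values, and reporting of side effects to the investigator is only encouraged.

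Two further inferences should be resisted. A reader might count the doses taken while a report waits and treat that as the size of the harm. The documents fix neither the interval between visits nor the share of women who would wait, and they do not say that one treated low reading should change the dose. A reader might also call it an error that a value of exactly 60 mg/dL is in range yet prompts carbohydrate. Treating at the lower edge of the range is a harmless, cautious margin.

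**Conclusion.** The point holds as a minor patient-safety improvement. Step 7 permits a low value to wait for the next visit, while the neighbouring paragraph instructs a call for hypoglycemia. The permission exists on either meaning; the difference between the instructions exists only if hypoglycemia means a low reading. The length of the wait and the number of women affected cannot be determined.

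The conclusion rests on the protocol text available to this review. If the unavailable material already requires a call for every low value, what remains is to bring step 7 into line with it.

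A reader might infer that women with low glucose are left without treatment instructions; the carbohydrate and emergency-care wording shows otherwise. A reader might also infer damage to the trial's comparisons, since maternal hypoglycemia is an outcome under Specific Aim 2. The documents do not support that: the rule is common to both arms, readings are to be recorded whichever reporting route is used, and no effect on that comparison has been shown. The efficacy result on drug failure is unaffected.

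**What to change.** In step 7, limit the next-visit option to high values and instruct a call to the clinic for any value below 60 mg/dL. This brings step 7 into line with the call that the next paragraph already instructs for hypoglycemia, and settles what to do about a low reading without symptoms. Check the patient information sheet and use the same wording there if it carries step 7.

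The cost is a text amendment with its ethics board submission, and a few more telephone calls to the clinic. There is no new data collection and no change to the sample size or the analysis.
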